### 4.13.6 Sensitivity Analysis

Sensitivity analyses will be based on the Efficacy Population.

# Final dosing regimen:

Subjects who received the final selected doses (7.5 mg/kg in subjects in 12 to  $\leq$ 36 months and 5 mg/kg in subjects <12 months) will be included in the following analyses.

- Daily change in RSV shedding in nasal swab samples determined using RT-qPCR from baseline through the treatment phase
  - Absolute change from baseline in RSV RNA viral load (outcome variable) will also be analyzed using MMRM as described in *Section 4.13.5*.
  - AUC for RSV RNA viral load measured in nasal swab samples by quantitative reverse transcription polymerase chain reaction (RT-qPCR) will be estimated via MMRM.
- Time to RSV RNA viral load being undetectable
  - The analyses are outlined in the time to event analyses as described in *Section 4.13.5*.

# Steroid Use:

The populations for analysis of steroid use are defined as follows:

- Subjects who received systemic corticosteroids at any time between 21 days prior to randomization and the PT 2 visit (Day 14).
- Subjects who did not receive systemic corticosteroids at any time between 21 days prior to randomization and the PT 2 visit (Day 14).

The following analyses will be analyzed descriptively for each of the above populations.

- Daily change in RSV shedding in nasal swab samples determined using RT-qPCR from baseline through the treatment phase
- AUC for RSV RNA viral load measured in nasal swab samples by quantitative reverse transcription polymerase chain reaction (RT-qPCR)
- Time to RSV RNA viral load being undetectable

Time to RSV RNA viral load being undetectable (TND) will be analyzed using two approaches as defined below:

- Time to RSV RNA viral load being undetectable (days) is defined as the time between the date of first dose to the first date during post-dose period of achieving RSV RNA viral load TND after which no further samples have detectable RSV RNA viral load. Subjects with baseline RSV viral load TND will be excluded from the analysis.
- Time to confirmed undetectable RSV RNA viral load (days) is defined as the time between the date of first dose to the first of 2 consecutive post-baseline time points of

achieving RSV RNA viral load TND. Subjects with baseline RSV viral load TND will be excluded from the analysis.

- Change from baseline of the Parent/Guardian ReSVinet total score which is defined as a sum of the score from each of the 7 parameters
- Parent/Guardian ReSVinet total score AUC will be calculated and summarized as described in *Section 4.13.2*.
- Time to resolution of RSV infection symptoms is defined as the time between the date of first dose to the first of 2 consecutive time points where each of the seven symptoms assessed by the Parent/Caregiver ReSVinet clinical scoring is 0 or 1. If a subject meets the resolution definition (0 or 1 score for 2 consecutive timepoints) at baseline and Day 2, then this subject will be excluded from the analysis.

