## **3.2.** Subject Exclusion Criteria

Subjects will not be eligible to participate in the study if they meet any of the following criteria:

- 1. Use of, or anticipated need for, invasive mechanical ventilation, cardiopulmonary bypass, hemodialysis, or extracorporeal membrane oxygenation; or subjects who are not expected to survive the current illness;
- 2. Subjects who have a medical history or a concurrent illness that in the opinion of the Investigator, might confound the results of the study or pose an additional risk in administering study drug to the subject, or that could prevent, limit, or confound the protocol-specified assessments. Examples include liver or renal insufficiency; significant cardiac, vascular, pulmonary, gastrointestinal, endocrine, neurologic, hematologic, rheumatologic, or metabolic conditions;

- 3. Subjects who are considered unable to take study drug orally,
- 4. Subjects who have received blood products within 6 months of study drug administration;
- Subjects with underlying immune deficiency (e.g., from confirmed human immunodeficiency virus infection or use of an immunosuppressive medication except immunoglobulin A deficiency);
- 6. Subjects who received (within 12 months before Screening) or who are currently on a waiting list for a bone marrow, stem cell, or solid organ transplant, or who received radiation or chemotherapy (within 12 months before screening);
- 7. Subjects who have had major surgery in the 6 weeks before randomization;
- 8. Subject receiving chronic oxygen therapy at home before admission;
- 9. Subjects who are being breastfed by a mother taking any of the excluded medications as noted in Section 5.9 (Prohibited Medication);
- 10. Subjects whose mother received an RSV vaccination while pregnant with the subject if they were born at term (≥37 weeks of gestation) and are less than 12 months of age;
- 11. Receipt of systemic antiviral, antifungal, or antimycobacterial therapy within 7 days of Screening;
- 12. Subjects who received systemic medications other than corticosteroids (either chronically [more than 14 days] or within 21 days before randomization) that are known to modulate the host's immune response or increase viral shedding, such as immunomodulatory therapies;
- 13. In Part 2, subjects dosed with an investigational or approved medication that is intended to prevent or treat RSV infection within the following times before the first dose of study drug:
  - ribavirin: 35 days,

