# 5.9. Prohibited Medications and Therapies

Systemic antiviral, antifungal, and antimycobacterial therapies are prohibited within 7 days of Screening and for the duration of the study.

The following are also prohibited:

- Systemic medications other than corticosteroids (either chronically [more than 14 days] or within 21 days before randomization and for the duration of the study) that are known to modulate the host's immune response or increase viral shedding, such as immunomodulatory therapies. In Part 2 only: Investigational or approved medication that is intended to prevent or treat RSV infection is prohibited within the following times before the first dose of study drug and for the duration of the study:
  - ribavirin: 35 days,
  - palivizumab: 100 days,
  - nirsevimab: 350 days,
  - other RSV specific monoclonal antibody: 5 half-lives of the specific antibody,
  - RSV vaccines: 12 months.

Note: If after enrollment the initiation of ribavirin is considered medically appropriate, please contact the Medical Monitor.

• Blood products within 6 months of study drug administration and for the duration of the study.

Breastfeeding mothers should also comply with the prohibited medication and therapies list.

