# 3.2 Endpoints

The primary efficacy endpoint is the daily change in RSV shedding in nasal swab samples determined using RT-qPCR from Baseline through the treatment phase in the pooled population (subjects from Part 1 and Part 2 together).

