Efficacy summary tables and figures will be presented by randomized treatment group and age group for Part 1 and Part 2 separately and will be labelled as follows. Additionally, efficacy summary tables and figures for efficacy endpoints for the pooled population will be summarized using pooled data (subjects from Parts 1 and 2) as appropriate. Other summaries including disposition, analysis populations, demographics, and baseline data will be displayed by treatment group, age group for Parts 1 and 2 separately. Parts 1 and 2 will also be pooled for these summaries.

Age Group:

- " $\geq 6$  to  $\leq 36$  months"
  - $\circ$  " $\geq 6$  to <12 months"
  - $\circ$  " $\geq 12$  to  $\leq 36$  months"
- " $\geq 28$  days to <6 months"
  - $\circ$  " $\geq$ 28 days to <3 months"

 $\circ$  " $\geq$ 3 to <6 months"

Treatment:

- "EDP-938"
- "Placebo"

Study Part:

- "Part 1"
- "Part 2"
- "Parts 1 and 2"

Safety summary tables and figures will be summarized separately for Part 1 and Part 2 as well as pooled Parts 1 and 2 data by the actual treatment group. In addition, pooled Parts 1 and 2 data will be summarized by age group.

For the reporting of this study both CDISC SDTM (SDTM Implementation Guide version 3.3 or later) and ADaM (ADaM Implementation Guide version 1.1 or later) standards will be applied. A subject will be considered to have completed the study after his/her attendance at the last planned study visit (Day 28  $\pm$  4 day), or the last unscheduled visit (if any occur), as applicable. For each subject his or her study completion status (Yes/No) is recorded on the End of Study CRF.

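### The steroid-use sensitivity sets are defined partly by corticosteroid use after randomisation, so arm-by-arm summaries within each set are open to bias.

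*SAP*

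**What the plan says.** SAP 4.13.6 opens by stating that "Sensitivity analyses will be based on the Efficacy Population". Under Steroid Use it defines two sets:

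- Users: "Subjects who received systemic corticosteroids at any time between 21 days prior to randomization and the PT 2 visit (Day 14".
- Non-users: "Subjects who did not receive systemic corticosteroids at any time between 21 days prior to randomization and the PT 2 visit (Day 14".

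It then says "The following analyses will be analyzed descriptively for each of the above populations". The outcomes listed are daily viral-load change, viral-load AUC, time to undetectable virus, and the Parent/Guardian ReSVinet change, AUC and time to symptom resolution. No test or model is named for these sets.

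SAP 4.1 fixes the layout of efficacy output: "Efficacy summary tables and figures will be presented by randomized treatment group and age group for Part 1 and Part 2 separately", with pooled tables added. The primary endpoint in SAP 3.2 is "daily change in RSV shedding in nasal swab samples determined using RT-qPCR from Baseline through the treatment phase in the pooled population".

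Steroids may be started on study. Protocol 3.2, criterion 12, covers "Subjects who received systemic medications other than corticosteroids", and Protocol 5.9 repeats the exception for the on-study prohibition: "Systemic medications other than corticosteroids (either chronically [more than 14 days] or within 21 days before randomization and for the duration of the study".

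The coinfection sets, also in SAP 4.13.6, are fixed at baseline. The SAP gives no reason for treating steroids differently and no caution on how to read the steroid tables.

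**The concern.** A steroid started after dosing is plausibly a response to the child's clinical course, which treatment may alter. Sorting children by such use conditions on something that happens after randomisation, so the two arms within a set need not be alike in prognosis. Three features make this concrete:

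- Some listed outcomes are symptom scores, so the reason for starting a steroid and the outcome can overlap.
- The treatment phase ends on Day 5 and the classification window on Day 14, 9 days later. A child first given a steroid on Day 10 counts as a user in the Day 3 and Day 5 results.
- A child who leaves early has less time in which to be classed as a user.

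At stake is how the tables are read. A within-set difference between arms could depart from the overall result even if steroids had no effect on the virus, and could then be taken as evidence that steroids modify the antiviral effect.

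**Working it through.** **Planned numbers (SAP 2.1, 2.2 and 4.2).** Part 1: 2 cohorts × 2 age groups × 12 = 48. Part 2: 2 age groups × 20 = 40. The total is 88, which agrees with the stated figure of approximately 90. At 2:1 in Part 1 and 4:1 in Part 2, EDP-938 has 32 + 32 = 64 children and placebo 16 + 8 = 24.

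**What the documents do not give.** There is no steroid-use rate, no effect of EDP-938 on steroid use, no link from severity to viral load and no viral-load SD. Every input below is an assumption.

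**Model.** Let T be 1 for EDP-938 and S a standard-normal severity.

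- Viral-load change: y = -2 - 0.5T + 0.6S + e, with e of SD 1.2. The true effect is -0.50 log10, and steroids have no effect on the virus.
- Steroid use: S + u - 0.6T > 0.8, with u of SD 0.7. The SD of S + u is √(1 + 0.49) = 1.2207.

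**Users.** The cut-offs in SD units are 0.8/1.2207 = 0.655 on placebo and 1.4/1.2207 = 1.147 on drug, giving 26% and 13% use. The normal-tail ratios φ(z)/(1 - Φ(z)) are 1.257 and 1.644. Mean severity among users is higher on drug by (1.644 - 1.257)/1.2207 = 0.317, so the bias is 0.6 × 0.317 = +0.19 log10.

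**Non-users.** The ratios φ(z)/Φ(z) are 0.433 and 0.236. The bias is 0.6 × (0.433 - 0.236)/1.2207 = +0.10 log10.

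Simulation of the same model gives -0.31 in users and -0.40 in non-users, and -0.50 in all children together. The shift therefore comes from the set definition alone. Varying the inputs:

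| Assumption | Users | Non-users |
|---|---|---|
| As above | -0.31 | -0.40 |
| Treatment shift in steroid use halved (0.3) | -0.41 | -0.45 |
| Severity effect on viral load halved (0.3) | -0.40 | -0.45 |
| Both halved | -0.45 | -0.47 |
| Treatment does not change steroid use | -0.50 | -0.50 |
| Steroid use not tied to severity | -0.50 | -0.50 |

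A second model used logistic steroid use, a base rate of 15% or 30%, a log-odds of 1 per SD of severity, a treatment log-odds of -0.5 or -1.0, a severity coefficient of 0.6 and a residual SD of 0.8. Its bias was +0.04 to +0.09 in users and +0.03 to +0.07 in non-users. With either link set to zero, bias was at most 0.01, which is simulation error. With sets that treatment cannot influence, it was 0.00 in both.

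**Precision, at 13% and 26% use.** The user set holds 64 × 0.13 = 8.3 and 24 × 0.26 = 6.2 children. With SD 1.2, the standard error of the difference is 1.2 × √(1/8.3 + 1/6.2) = 0.64 log10. For non-users (55.7 and 17.8) it is 1.2 × √(1/55.7 + 1/17.8) = 0.33 log10. Both exceed the largest biases above, 0.19 and 0.10. At 10% to 30% use regardless of arm, the user set would hold about 2 to 7 placebo and 6 to 19 EDP-938 children across both parts.

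**The case against.** The strongest reply is that no treatment comparison is planned here. The steroid analyses are descriptive, whereas the final-dosing-regimen analysis in the same section explicitly calls the MMRM. The inferential comparison sits in SAP 4.13.5 and does not use these sets. The SAP states no purpose for the steroid split, and describing children never exposed to steroids through follow-up is a legitimate aim that a pre-dose split would not serve. The sets will be very small, and concomitant medications are already to be tabulated (SAP 4.10; by treatment group in Protocol 11.5.7).

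Much of this stands, and it limits the weight of the point. It does not remove it. The SAP 4.1 layout still invites an arm-to-arm reading, and a descriptive label does not make the arms comparable. The general medication tables also do not isolate steroid use after dosing, because SAP 4.10 counts a drug started before dosing and continued afterwards as concomitant. The wish to describe unexposed children can be met by keeping the existing split as a labelled supplement.

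A reader might infer more: that these comparisons are biased, by 38% in users (0.19/0.50) and 19% in non-users. The documents do not support that. Those figures need the drug to halve steroid use and severity to drive both steroid use and viral load, and none of this is stated anywhere. The bias is zero if treatment does not change steroid use, or if steroid use is unrelated to prognosis and outcome. Its direction is assumed too: reversing one of the assumed signs reverses it. Children classed as users on pre-randomisation use alone do not raise the problem.

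**Conclusion.** The point holds in limited form. Both steroid sets depend partly on use after randomisation, so within-set summaries by arm are not protected by randomisation and are open to bias. Bias requires that treatment changes steroid use and that steroid use is tied to prognosis or outcome. Under the inputs tried it runs from 0 to about 0.19 log10 towards no effect, against a true effect of -0.50. That range is illustrative, since the documents supply none of the inputs. Sampling error in sets of this size is likely to be larger.

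The primary pooled analysis is unaffected, and a reader should not infer otherwise. The change is worth making because, as defined, the tables can differ from the main result when steroids do nothing, and the remedy is cheap.

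**What to change.** In SAP 4.13.6, define the two sets by systemic corticosteroid use from 21 days before randomisation to before the first dose. The data are already collected: Protocol 5.8 requires prior medications to be recorded back to 1 month before the first dose. Add a table of post-dose systemic corticosteroid use by arm.

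If the through-Day-14 split is kept, label it as a supplementary description and state that it does not support a treatment comparison.

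The cost is SAP wording and one table. The steroid set will be smaller, and some children in the no-steroid set will receive steroids after dosing, possibly within the treatment phase. That set therefore describes children without prior use, not children unexposed throughout, and the table title should say so.

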# **Coinfection:**

The populations for analysis of viral coinfection are defined as follows:

- Subjects who had a viral coinfection at baseline. Viral coinfection is defined as subjects who were infected with RSV and other pathogens at baseline.
- Subjects who were infected with RSV only (did not have a viral coinfection) at baseline.

The following analyses will be analyzed descriptively for each of the above populations.

- Daily change in RSV shedding in nasal swab samples determined using RT-qPCR from baseline through the treatment phase
- AUC for RSV RNA viral load measured in nasal swab samples by quantitative reverse transcription polymerase chain reaction (RT-qPCR)
- Time to RSV RNA viral load being undetectable

Time to RSV RNA viral load being undetectable (TND) will be analyzed using two approaches as defined below:

- Time to RSV RNA viral load being undetectable (days) is defined as the time between the date of first dose to the first date during post-dose period of achieving RSV RNA viral load TND after which no further samples have detectable RSV RNA viral load. Subjects with baseline RSV viral load TND will be excluded from the analysis.
- Time to confirmed undetectable RSV RNA viral load (days) is defined as the time between the date of first dose to the first of 2 consecutive post-baseline time points of achieving RSV RNA viral load TND. Subjects with baseline RSV viral load TND will be excluded from the analysis.
- Change from baseline of the Parent/Guardian ReSVinet total score which is defined as a sum of the score from each of the 7 parameters.

- Parent/Guardian ReSVinet total score AUC will be calculated and summarized as described in *Section 4.13.2*.
- Time to resolution of RSV infection symptoms is defined as the time between the date of first dose to the first of 2 consecutive time points where each of the seven symptoms assessed by the Parent/Caregiver ReSVinet clinical scoring is 0 or 1. If a subject meets the resolution definition (0 or 1 score for 2 consecutive timepoints) at baseline and Day 2, then this subject will be excluded from the analysis.

### 4.14 Safety Analyses

Statistical Analysis Plan,

Statistical methods for the safety analyses will be primarily descriptive in nature. The SAF will be used for all safety analyses, unless stated otherwise. Part 1 and Part 2 will be summarized separately and pooled. In addition, pooling of Parts 1 and 2 will be summarized by age group.

### 4.14.1 Adverse Events

Adverse events will be summarized by the Medical Dictionary for Regulatory Activities (MedDRA) Version 26.1 or higher, using the SOC and PT. All subjects in the SAF Population will be included in the summaries. AEs will be classified as pre-treatment AEs and treatment emergent adverse events (TEAEs) and are defined as follows:

- Pre-treatment AE: A pre-treatment event is any event that meets the criteria for an AE/SAE and occurs after the subject signs the ICF but before receiving the first administration of study drug.
- TEAE: A TEAE is defined as an AE occurring or worsening on or after the first dose of study drug.
- Treatment-Related TEAEs: TEAE will be defined as related if causality is related or possibly related. TEAEs where the causality is missing will be assumed to be related for table summary. However, it is displayed as missing in the listing.
- Grade AEs: Grade AEs in accordance with the NCI/CTCAE Version 5.0 scale as follows: Mild (Grade 1), Moderate (Grade 2), Severe (Grade 3), Life-threatening (Grade 4), Fatal (Grade 5).

Where a subject has the same adverse event, based on PT, reported multiple times, the subject will only be counted once at the PT level in adverse event frequency tables. Where a subject has multiple adverse events within the same SOC, the subject will only be counted once at the SOC level in adverse event frequency tables. When reporting adverse events by severity, in addition to providing a summary table based on the event selection criteria detailed above, summary table will also be provided based on the most severe event - independent of relationship to study treatment. Missing severity will be presented as severe for table summary. However, it is displayed as missing in the listing. All AEs will be presented in tables in descending order from the SOC with the highest total incidence (across all treatment groups) to the SOC with the lowest total incidence. Within each SOC, AEs will be sorted in alphabetical order of PT.

Summaries of TEAEs will include the following at a minimum:

- Overall summary of subjects with any TEAEs with a line for each of the following categories
  - o TEAEs
  - Study Drug-Related TEAEs
  - TEAEs of Grade 3 or Higher
  - TEAEs by Maximum Severity (Grades 1 to 5)
  - TEAEs leading to study drug discontinuation
  - TEAEs leading to study discontinuation
  - AEs leading to death
  - Serious TEAEs
  - Study Drug-Related Serious TEAEs

The above categories will also be summarized by SOC and PT.

# 4.14.2 Clinical Laboratory Data

Laboratory assessments will be reported as observed and change from baseline across scheduled visits, and as the incidence rate of shift change from baseline. 'Shift from baseline' tables will be generated for selected analytes. Laboratory shifts will be displayed as treatment-emergent abnormal, high, or low results. The following details the summary types where LLN = lower limit of normal and ULN = upper limit of normal.

For categorical tests: Treatment-emergent abnormal is defined as a change from normal at baseline to abnormal at any post-baseline visit.

Laboratory assessment grading is to be based on National Institute of Allergy and Infectious Diseases Division of AIDS (DAIDS) Table for Grading the Severity of Adult and Pediatric Adverse Events Version 2.1 dated July 2017. Lab grading will be coded as follows:

Grade 1=Mild, Grade 2=Moderate, Grade 3=Severe, Grade 4=Potentially Life-threatening.

Shift from baseline by DAIDS Grading will be summarized for selected chemistry and hematology parameters. Also, DAIDS Grading will be included in the chemistry and hematology listings.

In addition to DAIDS grading, selected laboratory parameters that are not graded by DAIDS will be displayed using the following custom laboratory shift reports:

• Treatment-emergent high is defined as a change from a result less than or equal to the high limit at baseline to a value greater than the high limit at any time post-baseline.

Results will be reported according to any value greater than the high limit, any value greater than  $2 \times$  ULN and  $3 \times$  ULN.

• Treatment-emergent low is defined as a change from a result greater than or equal to the low limit at baseline to a value less than the low limit at any time post-baseline.

Results will be reported to any value less than the LLN, less than  $(\frac{1}{2}) \times$  LLN and  $(\frac{1}{3}) \times$  LLN.

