#### 11.5.4. Clinical Laboratory Data

Laboratory assessments will be reported as mean change from Baseline across scheduled visits, and as the incidence rate of shift change from Baseline. Shift from Baseline tables will be generated for each treatment group for selected analytes. Laboratory shifts will be displayed as treatment-emergent abnormal, high, or low results. The following details the summary types where LLN = lower limit of normal and ULN = upper limit of normal.

For categorical tests: Treatment-emergent abnormal is defined as a change from normal at Baseline to abnormal at any post-Baseline visit.

For continuous tests:

• Treatment-emergent high is defined as a change from a result less than or equal to the high limit at Baseline to a value greater than the high limit at any time post-Baseline.

Results will be reported according to any value greater than the high limit, any value greater than  $2 \times$  ULN and  $3 \times$  ULN.

• Treatment-emergent low is defined as a change from a result greater than or equal to the low limit at Baseline to a value less than the low limit at any time post-Baseline.

Results will be reported to any value less than the lower limit, any value less than  $2 \times$  LLN and  $3 \times$  LLN.

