# 4. STATISTICAL CONSIDERATIONS

# 4.1 General Considerations

All statistical procedures will be completed using SAS version 9.4 or higher.

Continuous variables will be summarized using descriptive statistics (i.e., n, mean, standard deviation (SD), median, 25th percentile, 75th percentile, minimum and maximum values). The mean, median and the percentiles will be rounded to one decimal place beyond the precision of the values being summarized; the SD will be rounded to 2 additional decimal places beyond this precision and the minimum and maximum values will be displayed in the same precision. If n=0, then display n and leave all other statistics blank. If n=1, display "N/A" for SD.

Categorical variables will be summarized using frequency counts and percentages. The denominator for the percentages will be the number of subjects in the appropriate age group and treatment group within the analysis set of interest, unless otherwise specified. The denominator will be displayed when needed and the percentage will be rounded to one decimal place. If the frequency is 0, the percentage will not be displayed. A row denoted "Missing" will be included in count tabulations where specified on the shells to account for dropouts and missing values where applicable.

All subject data, including those derived, will be presented in individual subject data listings. Unless otherwise stated, unscheduled visit results will be included in date/time chronological order, within subject listings. All listings will be sorted by study part, treatment group, subject number, date/time and visit. The treatment group (randomized) as well as subject's sex, race, age and age group will be stated on each listing. Unless otherwise stated, data listings will be based on all subjects randomized.

Baseline, unless otherwise specified, will be defined as the last non-missing assessment collected before or on the date of first dose of study drug. For analyses of nasal swab data and analyses of RSV-related signs and symptoms, if assessments before the first dose of study drug are not available, a post treatment assessment collected no more than 60 minutes after the first dose of study drug will be used as the baseline value.

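### For categorical tests and parameters not graded by DAIDS, a child already beyond a limit at baseline cannot be counted as treatment-emergent in that direction, and no at-risk denominator is stated

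*SAP*

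**What the plan says.** SAP 4.14.2 describes two systems for laboratory shifts.

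- **Graded parameters.** "Shift from baseline by DAIDS Grading will be summarized for selected chemistry and hematology parameters". The grades also appear in the chemistry and hematology listings.
- **Ungraded parameters.** "selected laboratory parameters that are not graded by DAIDS will be displayed using the following custom laboratory shift reports". For these, "Treatment-emergent high is defined as a change from a result less than or equal to the high limit at baseline", to a later value above that limit. Likewise, "Treatment-emergent low is defined as a change from a result greater than or equal to the low limit at baseline", to a later value below it. The results are then broken down at ULN, 2 x ULN and 3 x ULN, or at LLN, one half LLN and one third LLN.

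Categorical tests have their own rule: "Treatment-emergent abnormal is defined as a change from normal at baseline to abnormal at any post-baseline visit".

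Protocol 11.5.4 has the same categorical rule. It opens its high rule with "Treatment-emergent high is defined as a change from a result less than or equal to the high limit at Baseline" and applies the high and low rules to continuous tests generally, with no DAIDS grading. It prints the low multiples as 2 and 3 times LLN, where the SAP has one half and one third.

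On denominators, SAP 4.1 sets a default: "The denominator for the percentages will be the number of subjects in the appropriate age group and treatment group". The sentence goes on to limit this to the relevant analysis set and to allow exceptions. SAP 4.14 makes that set the Safety Population. SAP 4.14.2 states no exception, and SAP Section 1 places the table shells in a separate document.

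**The concern.** The multiples of ULN and LLN are there to show how severe a laboratory change was. Under these definitions a child who starts just past the first limit cannot enter the more severe lines, however far the value moves. The adverse event tables use a different standard: "A TEAE is defined as an AE occurring or worsening on or after the first dose of study drug".

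The default denominator adds a second problem. It keeps children who cannot have the event because they were already beyond the limit, and children who were never tested. Protocol 8.11 makes untested children likely for some analytes. Urinalysis is limited to children who can give a specimen or who already have a catheter or collection bag, and cardiac biomarkers depend on the blood volume allowed.

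Safety against placebo, including laboratory results, is a Part 1 primary endpoint (protocol 2.2.1, SAP 3.2.1), and this is the first study of the drug in children (protocol 4.4). The safety analysis is descriptive, so the displayed counts and percentages are themselves the evidence.

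**Working it through.** **1. The rule applied to test cases.** Values are multiples of ULN, with LLN placed at 0.5 x ULN for illustration. The rule counts a child if baseline is at most 1 and a later value exceeds 1.

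| Baseline | Later value | Treatment-emergent high? |
|---|---|---|
| 0.8 (normal) | 3.5 | Yes |
| 0.4 (below LLN) | 1.2 | Yes |
| 1.1 or 1.2 (above ULN) | 3.5 | No, in none of the three lines |

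The excluded children are those already beyond the same limit. A low baseline still qualifies for the high rule.

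**2. Group sizes.** SAP 4.2 plans 12 children per cohort, two cohorts and two age groups in Part 1, and 20 per age group in Part 2. That is 12 x 2 x 2 + 20 x 2 = 48 + 40 = 88, which agrees with the stated figure of approximately 90. At 2:1 and 4:1 the EDP-938 group is 32 + 32 = 64 and the placebo group is 16 + 8 = 24. Within one age group this is 32 and 12.

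**3. Effect of the default denominator.** Let q be the incidence among at-risk children and b the share already beyond the limit at baseline. With every child in the denominator, the displayed percentage is q x (1 - b). The documents give neither quantity. Assume q = 20%:

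- b = 0: 20.0%
- b = 10%: 0.20 x 0.90 = 18.0%
- b = 20%: 0.20 x 0.80 = 16.0%
- b = 30%: 0.20 x 0.70 = 14.0%
- b = 40%: 0.20 x 0.60 = 12.0%

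An at-risk denominator gives 20% throughout. The relative shortfall equals b. At b = 20% about 51 EDP-938 and 19 placebo children are at risk (64 x 0.8 = 51.2; 24 x 0.8 = 19.2).

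**4. Missing pairs.** If a share m has no paired result, the display becomes q x (1 - b) x (1 - m). With m = 10%, also an assumption, it runs from 0.20 x 0.90 x 0.90 = 16.2% at b = 10% to 0.20 x 0.60 x 0.90 = 10.8% at b = 40%. Missing pairs alone (b = 0) give 18% at m = 10%. For a test done in only one child in ten (m = 90%) they give 0.20 x 0.10 = 2%.

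**5. Comparison between arms.** Suppose both arms have an at-risk incidence of 20%, but by chance b is 20% on EDP-938 and 40% on placebo. The display is 0.20 x 0.80 = 16% against 0.20 x 0.60 = 12%, a 4-point difference with no difference in risk. The opposite imbalance would reverse it.

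**The case against.** The strongest case against the point has five parts.

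- **Scope.** In the SAP the high and low rule covers only a subset of parameters that DAIDS does not grade, and the plan lists neither that subset nor the graded one. The gap may touch few important analytes. This stands as a limit on size. It does not help the categorical tests or the wider protocol rule.
- **Other displays.** Someone might infer that worsening from an abnormal baseline is never counted. The documents do not support that. DAIDS shift tables show, for example, a move from Grade 1 to Grade 3. Observed values and changes from baseline are summarised without a baseline restriction, all data are listed, and clinically significant findings become adverse events, where worsening counts. What remains is narrower. DAIDS tables cannot cover parameters that DAIDS does not grade, a mean change can conceal one large rise, and the adverse event route depends on the investigator's opinion (protocol 8.11).
- **Not a contradiction.** The adverse event tables and the laboratory shift tables are separate displays, so their different definitions can coexist. That is right. The comparison shows only that the plan recognises worsening elsewhere.
- **Denominator.** The SAP 4.1 default yields to any exception, and the shells may contain one. That is also right, so the denominator part is conditional. As a share of all treated children, the default percentage is correct. It is low only as a measure of incidence among tested, at-risk children.
- **Both arms alike.** Randomisation balances baseline abnormality in expectation, so the ratio between arms is unchanged on average. Chance imbalance remains plausible with 24 placebo children.

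The lines at 2 x and 3 x ULN might also be read as ignoring baseline. They sit under the definition, and the text does not release them from it.

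**Conclusion.** The point holds in a limited form. For categorical tests and the ungraded custom reports in the SAP, and for all continuous tests in protocol 11.5.4, a child already beyond a limit cannot be counted as treatment-emergent in that direction, even on reaching the more extreme multiples. No other planned display supplies an objective count for these parameters. Unless the shells differ, percentages will also fall below the incidence among tested, at-risk children.

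The size is unknown. The 18% to 12% range rests on an assumed at-risk incidence of 20% and an assumed 10% to 40% abnormal at baseline. The documents supply neither figure. Two further inferences should be avoided. The first is that only children within range qualify, since a low baseline can still become high. The second is that the tables favour EDP-938, since the direction between arms is not determined. No hypothesis test, alpha or power is affected. The change is still worth making, because it is cheap and alters displayed counts for a Part 1 primary safety endpoint.

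**What to change.** In SAP 4.14.2:

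- Define treatment-emergence separately for each cut (ULN, 2 x and 3 x ULN; LLN, one half and one third LLN): a post-baseline value beyond the cut when the baseline value was not beyond that same cut.
- Use as denominator the children with a baseline and at least one post-baseline result for that analyte who were not already beyond that cut, and display it.
- Categorical tests have no cut. Keep the normal-baseline rule, use children with paired results and a normal baseline as the denominator, and add a row for worsening from an abnormal baseline where results are ordered.
- Align protocol 11.5.4, including its low multiples.

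A child moving from 1.1 to 3.5 x ULN would then appear in the 2 x and 3 x lines. One moving from 1.1 to 1.9 x ULN crosses no new cut and would still appear only in the change-from-baseline summaries and listings.

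The cost is wording, minor programming, smaller denominators that differ by analyte, and slightly less favourable displayed rates. Protocol 11.2 allows such SAP changes only before unblinding, so this should be settled by then.
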